### Inclusion /Exclusion Checklist

INCLUSION CRITERIA			
Signed consent form		 YES	 NO
Age ≥ 30 years		 YES	 NO
Framingham Risk Score of 10-15% [FRS = _____ ]		 YES	 NO
HIV positive		 YES	 NO
Stable cART regimen for ≥ 6 months		 YES	 NO
HIV viral load <200copies/ml for ≥ 6 months		 YES	 NO
 EXCLUSION CRITERIA			
Coronary heart disease (CHD), stroke or PVD		 YES	 NO
Family history of CHD < 55 in a male first degree relative		 YES	 NO
Family history of CHD <65 in a female first degree relative		 YES	 NO
Type 2 Diabetes		 YES	 NO
Familial hypercholesterolaemia		 YES	 NO
Aboriginal or Torres Strait Islander people with LDL-C >2.5 mmol/L		 YES	 NO
Blood pressure ≥ 180/110		 YES	 NO
HDL-C < 1 mmol/L and total cholesterol > 6.5 mmol/L		 YES	 NO
Documented history of:			
Ischemic stroke or transient ischemic attack (TIA)		 YES	 NO
Peripheral arterial disease (regardless of severity)		 YES	 NO
Congestive heart failure		 YES	 NO
Coronary artery disease or ECG findings consistent with prior MI		 YES	 NO
Carotid artery stenosis or >50% occlusion of carotid artery known previously or discovered during screening procedures		 YES	 NO
Total cholesterol >7.5 mmol/L		 YES	 NO

Triglyceride level > 4 mmol/L		 YES	 NO
HDL-c <1mmol/l and total cholesterol >6.5mmol/l		 YES	 NO
Current or prior (last 6 months) statin therapy		 YES	 NO
Current or prior (last 6 months) use of ezetimibe		 YES	 NO
Current or prior (last 6 months) use of fibrates or niacin		 YES	 NO
Pregnancy or lactation		 YES	 NO
Hypersensitivity to statins		 YES	 NO
Known myopathy or baseline CK > 3x ULN		 YES	 NO
Contraindicated concurrent medication (to statin use)		 YES	 NO
Current cyclosporine, fusidic acid or oral corticosteroid use		 YES	 NO
Concomitant antiplatelet drug		 YES	 NO
Unable to complete study procedures (i.e. attendance at AH for cIMT and cPWV testing or cIMT images not accepted for analysis despite redo examination)		 YES	 NO
Concomitant renal or hepatic disease, defined as the presence of the following:		 YES	 NO
    Creatinine clearance <30 ml/min [CCL = _____ ]		 YES	 NO
    Transaminases (ALT, AST) >3x the upper limit of normal		 YES	 NO
    Acute hepatic failure		 YES	 NO
    Compensated cirrhosis Child Class B or C		 YES	 NO
Other active significant disease		 YES	 NO
- Describe	_____		
Eligible for Trial?		 YES	 NO

Completed by: \_\_\_\_\_

Signed \_\_\_\_\_

Date / /

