### Exclusion criteria

1. Recommended use of lipid lowering drug therapy according to Australian Guidelines (National heart foundation 2012)
2. Family History of myocardial infarction or stroke
3. Type 2 Diabetes
4. Familial hypercholesterolemia
5. Aboriginal or Torres Strait Islander people with LDL-C >2.5 mmol/L
6. Blood pressure  $\geq$  180/110
7. Documented history of:
  - a. Ischemic stroke or transient ischemic attack (TIA)
  - b. Peripheral arterial disease
  - c. Congestive heart failure
  - d. Coronary artery disease or ECG findings consistent with prior MI
8. Carotid artery stenosis or >50% occlusion of the carotid artery
9. Total Cholesterol > 7.5 mmol/L
10. Triglyceride level >4.0 mmol/L
11. HDL-c <1 and Total cholesterol > 6.5 mmol/L
12. Current or prior (last 6 months) statin, ezetimibe, fibrate or niacin therapy

13. Contraindication to statin use
  - a. Pregnancy or lactation
  - b. Hypersensitivity to statins
  - c. Known myopathy or baseline CK > 3x ULN
  - d. Contraindicated concurrent medication
  - e. Current cyclosporine, fusidic acid or oral corticosteroid use
14. Concomitant antiplatelet drug
15. Unable to complete study procedures
16. Any active, clinically significant disease
17. Concomitant renal or hepatic disease, defined as the presence of the following:
  - a. Creatinine Clearance <50ml/min
  - b. Transaminase (ALT, AST) above 3 times upper normal limit
  - c. Acute hepatic failure
  - d. Compensated cirrhosis Child Class B or C

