### 9.2 Exclusion criteria

1. Recommended use of lipid lowering drug therapy according to Australian Guidelines (National heart foundation 2012)
2. Family History of myocardial infarction or stroke in a male first degree relative before 55 years of age, or a female first degree relative before 65 years of age
3. Type 2 Diabetes
4. Familial hypercholesterolemia
5. Aboriginal or Torres Strait Islander people with LDL-C >2.5 mmol/L
6. Blood pressure  $\geq$  180/110
7. Documented history of:
  - a. Ischemic stroke or transient ischemic attack (TIA)
  - b. Peripheral arterial disease (regardless of severity)
  - c. Congestive heart failure
  - d. Coronary artery disease or ECG findings consistent with prior MI
8. Carotid artery stenosis or >50% occlusion of the carotid artery known previously or discovered during screening procedures
9. Total Cholesterol > 7.5 mmol/L
10. Triglyceride level >4.0 mmol/L
11. HDL-c <1 and Total cholesterol > 6.5mmol/L
12. Current or prior (last 6 months) statin therapy

13. Current or prior (last 6 months) use of ezetimibe
14. Current or prior (last 6 months) use of fibrates or niacin
15. Contraindication to statin use
  - a. Pregnancy or lactation
  - b. Hypersensitivity to statins
  - c. Known myopathy or baseline CK > 3x ULN
  - d. Contraindicated concurrent medication
  - e. Current cyclosporine, fusidic acid or oral corticosteroid use
16. Concomitant antiplatelet drug (Aspirin, Abciximab, Anagrelide, Cilostazol, Clopidogrel, Dipyridamole, Eptifibatide, Ticagrelor, Ticlopidine, Tirofiban, Terutroban)
17. Unable to complete study procedures (i.e. attendance at AH for cIMT and cPWV testing or cIMT images not accepted for analysis despite redo examination)
18. Any active, clinically significant disease (including but not limited to; pancreatitis, significant psychiatric disorders, acquired immunodeficiency syndrome (AIDS) defining illnesses) which may impact on the results of the study, increase the risk of serious adverse events (SAE) or limit participants life expectancy to < 24 months
19. Concomitant renal or hepatic disease, defined as the presence of the following:
  - a. Creatinine clearance <50 ml/min (calculated using the Cockcroft-Gault equation)
  - b. Transaminase (ALT, AST) above 3 times upper normal limit
  - c. Acute hepatic failure
  - d. Compensated cirrhosis Child Class B or C

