### **Creatinine clearance**

An estimated creatinine clearance will be calculated at screening visit to determine eligibility for entry into the trial using the Cockcroft-Gault equation

$$\text{For men } Cl = \frac{1.23 \times \text{weight (kg)} \times (140 - \text{age (years)})}{\text{Creatinine } (\mu\text{mol/L})}$$

$$\text{For women } Cl = \frac{1.03 \times \text{weight (kg)} \times (140 - \text{age (years)})}{\text{Creatinine } (\mu\text{mol/L})}$$

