### 12.1.1 Eligibility

Clinical eligibility will be recorded based on the inclusion (1-6) and exclusion criteria (7-26) listed below.

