  - a. Creatinine clearance <50 ml/min (calculated using the Cockcroft-Gault equation)
  - b. Transaminase (ALT, AST) above 3 times upper normal limit
  - c. Acute hepatic failure
  - d. Compensated cirrhosis Child Class B or C

If the patient fulfils all eligibility criteria (1-26 above) then a baseline visit will be booked. CRFs from participants assessed but found to be ineligible for inclusion in the study will be entered into the database recording the reason for ineligibility.

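### The eligibility checklist excludes creatinine clearance only below 30 ml/min and asks for 6 months of stable ART, where the protocol sets 50 ml/min and more than 3 months

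*Combined protocol and SAP*

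**What the plan says.** The protocol body is consistent on renal function. The synopsis excludes "Creatinine Clearance <50ml/min". Section 9.2 excludes "Creatinine clearance <50 ml/min (calculated using the Cockcroft-Gault equation"), and section 12.3 repeats that as item 26a. Section 11.1 gives the purpose of the calculation: "An estimated creatinine clearance will be calculated at screening visit to determine eligibility for entry into the trial".

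It is equally consistent on antiretroviral stability. The synopsis and sections 9.1, 10.9.3 and 12.2 all require more than 3 months on a stable regimen.

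Section 12 ties entry to these criteria. Section 12.1.1 states: "Clinical eligibility will be recorded based on the inclusion (1-6) and exclusion criteria (7-26) listed below". Section 12.3 closes with: "If the patient fulfils all eligibility criteria (1-26 above) then a baseline visit will be booked".

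The checklist in Appendix 22.1.1 prints different rules. Its renal line is "Creatinine clearance <30 ml/min", beside a blank for the value. Its ART line is "Stable cART regimen for ≥ 6 months". It ends with the question "Eligible for Trial" and spaces for name, signature and date.

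**The concern.** A checklist that ends in an eligibility decision should reproduce the criteria that define eligibility. This one gives the person signing it a different rule on two thresholds, and the two errors run in opposite directions. The renal line is looser than the protocol, so it can admit patients whom the protocol keeps out of a statin trial. The ART line is stricter, so it can turn away eligible patients.

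At stake are avoidable eligibility deviations on one side and needless screen failures on the other. The trial plans 102 participants across as many as eight centres, and sections 15 and 16 name poor accrual among the grounds for stopping. Sites that work from section 12 would avoid both errors. Sites that work from the printed form would not.

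**Working it through.** **Step 1: line-by-line comparison.** The numbered criteria 1 to 26 in sections 12.2 and 12.3 were set against the checklist. These do not match:

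| Item | Protocol | Checklist | Effect |
|---|---|---|---|
| 26a | Excludes CrCl below 50 ml/min (Cockcroft-Gault) | Excludes CrCl below 30 ml/min | CrCl 30 to <50 passes the form, fails the protocol |
| 5 | Stable ART for more than 3 months | At least 6 months | Stable >3 to <6 months fails the form, meets the protocol |
| 7 | Excludes if lipid-lowering drugs are recommended by the Australian guideline | No line | Partly covered by the FRS, lipid, blood pressure and diabetes lines; the remainder cannot be determined because the guideline is not reproduced |
| 2 | Age above 30 | Age 30 or above | Minor: people aged exactly 30 |
| 8 | First-degree family history of infarction or stroke at the stated ages | CHD only | Minor: section 11 has family history of CVD asked at screening |

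That is 5 of 26 numbered items, or 5 of 25 distinct ones, since items 24 and 25 carry the same text. Items 26a and 5 are substantive threshold conflicts.

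**Step 2: the renal gap in serum creatinine.** Section 11.1 gives CrCl = k × weight × (140 − age) / creatinine, with k = 1.23 for men and 1.03 for women. Solved for the creatinine at a cut-off C:

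creatinine = k × weight × (140 − age) / C

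For any fixed sex, age and weight, the form's cut-off divided by the protocol's is 50/30 = 1.67. No assumption about the patient is needed.

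For illustration, with ages and weights assumed (the documents give no distribution):

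| Assumed patient | Protocol, C = 50 (µmol/L) | Form, C = 30 (µmol/L) |
|---|---|---|
| Man, 65 y, 60 kg | 1.23 × 60 × 75 / 50 = 110.7 | 184.5 |
| Man, 55 y, 70 kg | 1.23 × 70 × 85 / 50 = 146.4 | 243.9 |
| Man, 45 y, 90 kg | 1.23 × 90 × 95 / 50 = 210.3 | 350.6 |
| Woman, 65 y, 60 kg | 1.03 × 60 × 75 / 50 = 92.7 | 154.5 |
| Woman, 55 y, 70 kg | 1.03 × 70 × 85 / 50 = 122.6 | 204.3 |
| Woman, 45 y, 90 kg | 1.03 × 90 × 95 / 50 = 176.1 | 293.6 |

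A single case: a man of 60 weighing 70 kg with creatinine 150 µmol/L has CrCl = 1.23 × 70 × 80 / 150 = 45.9 ml/min. The protocol excludes him; the checklist line does not.

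**Step 3: what governs.** Sections 11.1, 12.1.1 and 12.3 make the protocol criteria decisive, and nothing in the documents reconciles the checklist with them. Both sides are current text, not amendment history.

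The documents have no stated figure to reproduce on this point, and the sample-size calculation does not depend on it.

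**The case against.** The strongest reply is that this is a clerical slip in an appendix template. The protocol text governs and is uniform wherever it states the two criteria. The clearance value is written down twice on the screening forms, so an error is visible to anyone who looks. The main screening page has its own eligibility question with no threshold attached. Section 19.4 provides for monitoring of protocol implementation at the Swiss sites. In the middle example, a man with creatinine of 146 to 244 µmol/L is at about 1.4 to 2.3 times the Melbourne upper limit of 105, and might be stopped under the line for other significant disease. The ART error only rejects; it exposes nobody. The start date of each current antiretroviral is recorded, so the 3-month rule can still be checked.

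Much of this stands as mitigation. It shows that mis-enrolment is not certain and that the consequence is limited. It does not make the form right. The only threshold printed beside the recorded clearance is 30, and no section assigns a second comparison with 50. The source-data check in section 19.4 covers at least 50 percent of enrolled subjects at Swiss sites. It compares source with CRF, which would not by itself reveal a wrong threshold on the CRF, and it does not target rejected patients. No equivalent is stated for Melbourne, where 72 of the 102 are planned. In smaller or older patients the creatinine can be near normal (111 µmol/L for the 65-year-old, 60 kg man at the protocol cut-off), so the general disease line is a weak safeguard.

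It is also fair that only two of the five differences have a demonstrated effect, and that the appendix copy is a blank form, so the documents do not show that anyone was screened on it.

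**Conclusion.** The concern holds: the checklist is wrong as written. Two thresholds conflict with a protocol body that is consistent throughout. The bands affected are CrCl from 30 to below 50 ml/min (wrongly passed) and stable ART for more than 3 but less than 6 months (wrongly failed). One exclusion has no line, and two further lines differ in minor ways.

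The number of patients in either band cannot be derived from the documents. The creatinine figures depend on the assumed ages and weights; the ratio of 1.67 does not. The documents do not show harm from 10 to 20 mg of rosuvastatin at the clearances in question. The mismatch operates before randomisation, so it biases neither arm, and the sample size, power and analysis are untouched. It merits correction because the form is where the decision is recorded and the correction costs almost nothing.

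**What to change.** Revise the checklist in Appendix 22.1.1 to match section 9:

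- renal exclusion at CrCl below 50 ml/min by Cockcroft-Gault;
- stable ART for more than 3 months, with the protocol's allowance for dose changes;
- age above 30;
- first-degree family history of myocardial infarction or stroke at the ages given in section 9.2;
- a new line for exclusion 1 of section 9.2 (guideline-recommended lipid-lowering therapy).

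It would be tidy to align the screening form's question on recent antiretroviral changes as well. It refers to a period of six, with the unit cut off in the text available, and it collects history rather than stating a criterion.

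If anyone has already been screened on the form as printed, compare each recorded CrCl with 50, confirm guideline status from the clinical notes (the checklist does not capture it), and review any rejection made on ART stability alone.

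The cost is one CRF revision and a short re-check of recorded values. No design, sample-size or analysis change is needed.

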**22.1.2 Baseline Visit**

Study number				
Date of Visit				____/____/____
Any new medical diagnosis since screening?				 Yes  No
If yes, list:				1.
				2.
				3.
				4.
Any new medications since last visit?				 Yes  No
If yes please detail below				
Trade Name	Generic Name	Daily Dose	Start Date	
1.				
2.				
3.				
Any medications ceased since last visit? If yes please detail below				 Yes  No
Trade Name				Generic Name
Daily Dose				Stop Date
1.				
2.				
3.				
Smoking status				 Non-smoker
				 Ex- Smoker
				 Current smoker
Has an adverse event occurred?				 Yes  No
If yes please complete adverse event				
Any new abnormalities on				 Yes  No
If yes list:				1.
				2.
				3.
Weight (kg)				
Blood Pressure				
Provided with 3/12 supply of				 Yes  No
Bloods taken?				 Yes  No

Completed by: \_\_\_\_\_ Signed \_\_\_\_\_

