### Demographic data, medical history and medication questionnaire

Patients will be questioned on details necessary for determining eligibility for entry into the trial and important study variables. Topics to be covered include, age, gender, race, presence of CVD risk factors (smoking status, family history of CVD etc.), past medical history, current medications and the presence of any allergies.

The questionnaire will be completed by a study investigator at the screening visit. At all subsequent visits patients will be asked:

1. If they have developed or been diagnosed with any new medical illnesses since the last review
2. If they have started or stopped any non-study medications
3. Their current smoking status.

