### **Adverse event assessment**

See sections 13 and 14 for details on AE and SAE reporting and assessment

At each study visit patients will be asked to report any untoward medical occurrences and will also be specifically questioned regarding the presence of:

- Myopathic symptoms (weakness, muscle pain)
- Gastrointestinal disturbance (diarrhoea, nausea, vomiting, abdominal pain)
- Jaundice

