#### **12.5 Baseline visit**

Participants will be required to present to the study site having fasted overnight for at least 12 hours (no food, caffeine or caloric drinks; free water is encouraged)

Assessments performed:

1. Targeted physical examination and updated history, assessment for new concomitant medications
2. Adverse event assessment
3. Laboratory assessments
  - a. Biochemistry
  - b. Fasting metabolic assessment
  - c. hsCRP
  - d. Markers of innate immunity and inflammation
  - e. Storage of plasma and PBMCs (\*Melbourne participants only) for possible further analysis in the future

Patients will be provided with a three (3) month supply of the study medication and educated regarding possible clinical signs of potential adverse events (muscle ache, fever, abdominal pain, jaundice, rash); regardless of randomisation. Patients will also be provided with contact details for study co-ordinators in case of adverse event.

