## **13 Adverse Events**

An AE is defined as follows:

Any untoward medical occurrence in a clinical investigation subject administered a medicinal product and which does not necessarily have a causal relationship with this treatment. An AE can therefore be any unfavourable and unintended sign, symptom, or disease temporally associated with the use of a medicinal product, whether or not considered related to the medicinal product.

Pre-existing or recurrent conditions that occur during the study should not be considered as AEs unless they change in frequency or severity.

All AEs that occur from the time the subject consents to participate in the study and throughout the duration of the study shall be recorded as an AE in the individuals CRF.

At the final study visit (week 96) any ongoing adverse events deemed related to study drug will be followed up for a minimum of 30 days and until resolution.

In case a treatment interruption is needed during the treatment period in the event of a suspected toxicity, the subject will not automatically be withdrawn from the trial, as long as treatment interruption does not exceed 4 weeks.

AEs and SAEs will be categorised and recorded as per the modified Division of AIDS table for grading the Severity of Adverse Events (see Appendix 22.6). Causal relationship of AEs and SAEs to the trial and the study medication will also be assessed.

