**22.1.3 Week 12 Visit**

Study number				
Date of Visit				____/____/____
Any new medical diagnosis since screening?				 Yes  No
If yes, list:				1.
				2.
				3.
				4.
Any new medications since last visit?				 Yes  No
If yes please detail below				
Trade Name	Generic Name	Daily Dose	Start Date	
1.				
2.				
3.				
Any medications ceased since last visit? If yes please detail below				 Yes  No
Trade Name				Generic Name
Daily Dose				Stop Date
1.				
2.				
3.				
Smoking status				 Non-smoker
				 Ex- Smoker
				 Current smoker
Has an adverse event occurred?				 Yes  No
Myopathic symptoms				 Yes  No
Gastrointestinal disturbance				 Yes  No
Jaundice				 Yes  No
If yes please complete adverse event				
Any new abnormalities on				 Yes  No
If yes list:				1.
				2.
				3.
Weight (kg)				
Blood Pressure				
Bloods taken?				 Yes  No

Completed by: \_\_\_\_\_ Signed \_\_\_\_\_

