**22.1.8 Unscheduled Visits**

Study Number	
Date of Visit	____/____/____ Time: ____:____ hr
Person initiating unscheduled	
Reason for unscheduled visit	
Adverse Event Assessment	
Onset date of Adverse Event	
Time of Onset (if Known)	
Description of Adverse event:	
Adverse Event Severity Grade (refer to Division of AIDS Table for grading of severity)	 Mild (Grade 1)
	 Moderate (Grade 2)
	 Severe (grade 3-4)
Is this a Serious Adverse Event	 Yes  No (If YES, please fill in the
Treatment for AE required? (If yes describe in detail)	 Yes  No
Related to the study drug?	 Confirmed
	 Probable
	 Possible
	 Excluded
	 Non -assessable
Study medication stopped	 Yes  No
Withdrawn from the study	 Yes  No
Outcome of Adverse Event	 Ongoing
	 Resolved
	 Unknown
Date of resolution of adverse	____/____/____ (If not ongoing)
Date subject will be next	

Completed by: \_\_\_\_\_ Signed \_\_\_\_\_

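### The baseline form omits the muscle, gut and jaundice prompts required at each visit, so section 13's test for pre-existing symptoms has no structured pre-dose comparator; the later forms also use the wrong look-back for diagnoses

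*Combined protocol and SAP*

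**What the plan says.** **Prompts.** Section 11 (Adverse event assessment) states: "At each study visit patients will be asked to report any untoward medical occurrences and will also be specifically questioned regarding the presence of" three things, namely muscle symptoms, gastrointestinal disturbance and jaundice. Section 12.5 lists "Adverse event assessment" among the baseline procedures, and the flow chart in section 5 marks it at week 0. On the baseline form (22.1.2) the only adverse-event item is "Has an adverse event occurred". The forms for weeks 12, 24, 48, 72 and 96 have the same item followed by yes/no boxes for "Myopathic symptoms", gastrointestinal disturbance and jaundice.

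**Rule for pre-existing complaints.** Section 13: "Pre-existing or recurrent conditions that occur during the study should not be considered as AEs unless they change in frequency or severity". Adverse events are recorded from consent.

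**Diagnosis look-back.** At visits after screening, section 11 (questionnaire) has patients asked: "If they have developed or been diagnosed with any new medical illnesses since the last review". The follow-up forms ask instead: "Any new medical diagnosis since screening". The medication items on those same forms look back to the last visit.

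**Analysis.** Secondary outcome 1 (section 7.2) is the rate of adverse effects, symptomatic and biochemical, in the two arms. Section 17 summarises it by frequency and percentage. It defines no treatment-emergent event and no rule for repeats.

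**The concern.** Muscle symptoms are the complaint of most interest with a statin, and section 10.8 describes mild myotoxicity as common. Many people report aches or loose stools without any drug. To separate those from a treatment effect, one needs the same question asked in the same way before and after dosing. Here the forms change the method of elicitation at the point where treatment starts: one general question before it, three named symptoms after it. In between, at the baseline visit, participants are taught to watch for muscle ache, abdominal pain and jaundice (section 12.5). Some complaints first recorded at week 12 may therefore be old ones.

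At stake is the clarity of the symptomatic part of secondary outcome 1, which section 15 also puts before the DSMB at the unblinded 48-week review. A prompted pre-dose answer can be collected only before the first dose.

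The look-back to screening is a smaller matter. A diagnosis made between baseline and week 12 would, if the wording is followed literally, be listed on all five follow-up forms.

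**Working it through.** The plan states no figure on this point, so there is none to reproduce. The check is mainly a comparison of texts.

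**1. Is baseline within section 11's requirement?** Yes. It is a study visit, and sections 5 and 12.5 both schedule an adverse-event assessment there.

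**2. Could the missing prompts be a text-extraction loss?** Unlikely. The cut-off line telling staff to complete an adverse-event record follows the general item directly on the baseline form. The same cut-off line appears on the later forms, after the three prompts.

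**3. What else records these symptoms before dosing?**
- The general baseline item asks about adverse events, which section 13 counts from consent. A long-standing ache is not one, so a correct answer can be no.
- The screening form takes past medical history with a tick box for active conditions, and a myopathy item. These capture diagnoses. Known myopathy is also an exclusion, so the item says little about randomised participants.
- The adverse-event record in 22.1.8 has "Onset date of Adverse Event", one severity grade, outcome and resolution date. It can place an onset before dosing, by recall. It has no frequency field and no earlier value for comparison.

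Section 13's test is a change in frequency or severity. For mild muscle and gut symptoms the forms give no structured starting value for either.

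**4. Illustration of what counting prevalent symptoms would do.**

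Inputs:
- 51 per arm, from 102 randomised 1:1.
- Excess e of 5% or 7% on active drug. This is an assumption: section 10.8 gives 5% to 7% as the rate among statin users, not a difference from placebo.
- Entry prevalence b of 5%, 10% or 20%. This is an assumption; the documents give none.
- Every prevalent symptom is wrongly counted, and there is no other background. Full miscounting makes this a worst case for the dilution from prevalent symptoms.

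Formulas: placebo rate p0 = b; active rate p1 = b + (1 − b)e; SE of the difference = √[p1(1 − p1)/51 + p0(1 − p0)/51].

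| e | b | p0 | p1 | Difference (points) | Ratio | SE (points) |
|---|---|---|---|---|---|---|
| 5% | 5% | 5.0% | 9.75% | 4.75 | 1.95 | 5.2 |
| 5% | 10% | 10.0% | 14.5% | 4.5 | 1.45 | 6.5 |
| 5% | 20% | 20.0% | 24.0% | 4.0 | 1.20 | 8.2 |
| 7% | 5% | 5.0% | 11.65% | 6.65 | 2.33 | 5.4 |
| 7% | 10% | 10.0% | 16.3% | 6.3 | 1.63 | 6.7 |
| 7% | 20% | 20.0% | 25.6% | 5.6 | 1.28 | 8.3 |

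Example, first row: p1 = 0.05 + 0.95 × 0.05 = 0.0975; ratio = 0.0975/0.05 = 1.95; SE = √[(0.0975 × 0.9025 + 0.05 × 0.95)/51] = 0.052.

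As b rises, both arms' rates rise, the ratio moves towards 1, the difference shrinks a little and its SE grows. Nothing in the mechanism favours one arm while blinding holds.

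**5. Where does the diagnosis list go?** On each form it is a separate field from the adverse-event item. Section 17 analyses no diagnosis counts. Repeats therefore affect the tidiness of the list, not a planned estimate.

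**The case against.** The strongest reply is that the protocol text already does the work. Section 11 tells staff to ask the three questions at every visit, whether or not the form has boxes for them. Section 13 excludes pre-existing and recurrent conditions that have not changed. The adverse-event record carries an onset date. Baseline includes an updated history and a targeted examination. For jaundice there are objective data: bilirubin and ALT are in the safety panel (section 11.2), and biochemistry is run at screening and baseline. CPK is measured then too, and a baseline CK above three times the upper limit is an exclusion.

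Much of this stands. It narrows the gap to a prompted pre-dose answer, mainly for mild muscle and gut symptoms. It does not close the gap, because an instruction to ask without a place to write the answer leaves nothing to compare with later.

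A reader might infer several stronger things that the documents do not support:
- *That old and repeated complaints enter the adverse-event record as new.* Section 13 and the onset date are there to screen them out. The fair statement is that some may be counted.
- *That section 13 cannot be applied at all.* It can, from history and recall, but without a structured comparator.
- *That the look-back to screening inflates adverse-event counts.* It governs the diagnosis list only.
- *That a definite loss of precision can be quoted.* Any such figure needs an entry prevalence that the documents do not give, and would treat the on-statin rate in section 10.8 as an excess over placebo. No interval or test for adverse events is planned. In the table the difference is at most about 1.2 times its SE (6.65/5.4), so this trial would not resolve an excess of this size even at the lowest prevalence shown.

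**Conclusion.** Both mismatches between the forms and section 11 are real. The omitted baseline prompts mean that, on the forms, symptoms are prompted only after dosing begins, and that a change in frequency or severity has no structured pre-dose reference. The likely effect is some counting of prevalent mild muscle and gut symptoms in both arms. That adds noise and dilutes the relative contrast in secondary outcome 1. It does not by itself favour rosuvastatin or placebo, and it does not touch the primary endpoint.

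The size cannot be fixed from the documents. The ratios above (1.95 falling to 1.20, or 2.33 falling to 1.28) only illustrate the direction; they rest on assumed prevalences, an assumed excess and full miscounting. The look-back wording is a separate, minor inconsistency that can duplicate diagnosis entries.

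This is a modest data-collection fault, worth correcting because the correction is cheap and the baseline answer cannot be collected in the same way once dosing has started.

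**What to change.** 1. Add the three prompts to the baseline form, each with severity grade and frequency, completed before the first dose. Record the same two items when a prompt is answered yes at follow-up; the adverse-event record now has a grade but no frequency field.
2. On the week 12, 24, 48, 72 and 96 forms, ask for new diagnoses since the last visit, in line with section 11 and with the medication items on those forms. On the baseline form the reference to screening is correct.
3. In section 17, count a prompted symptom once per participant, when it is new or has increased in frequency or severity from baseline. Frequency must stay in the rule: one based on grade alone would conflict with section 13 and miss a symptom that becomes more frequent at the same grade.

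The cost is a form revision, a sentence in section 17 and about a minute per participant at a visit that already includes an adverse-event assessment. Participants already dosed cannot supply the baseline answer except by recall, so their records should be identified as lacking it.
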